9.2.4 Follow-up of AEs and SAEs

- Nonserious AEs should be followed to resolution or stabilization, or reported as SAEs if they become serious (see Appendix 3).
- Follow-up is also required for nonserious AEs that cause interruption or discontinuation of study intervention and for those present at the end of study intervention as appropriate.
- All identified nonserious AEs must be recorded and described on the nonserious AE page of the CRF (paper or electronic). Completion of supplemental CRFs may be requested for AEs and/or laboratory abnormalities that are reported/identified during the course of the study.

After the initial AE/SAE report, the investigator is required to proactively follow each participant at subsequent visits/contacts. All SAEs, and nonserious AEs of special interest (as defined in Section 9.2.1) will be followed until resolution, until the condition stabilizes, until the event is otherwise explained, or until the participant is lost to follow-up (as defined in Section 8.3).

Further information on follow-up procedures is given in Appendix 3.

9.2.5 Regulatory Reporting Requirements for SAEs

• Prompt notification by the investigator to the Sponsor of SAEs is essential so that legal obligations and ethical responsibilities toward the safety of participants and the safety of a product under clinical investigation are met.

• An investigator who receives an investigator safety report describing SAEs or other specific safety information (eg, summary or listing of SAEs) from the Sponsor will file it along with the Investigator's Brochure and will notify the IRB/ IEC, if appropriate according to local requirements.

The Sponsor or designee must report AEs to regulatory authorities and ethics committees according to local applicable laws and regulations. A SUSAR (suspected, unexpected serious adverse reaction) is a subset of SAEs and must be reported to the appropriate regulatory authorities and investigators in accordance with local and global guidelines and requirements.

9.2.6 Pregnancy

If, following initiation of the study intervention, it is subsequently discovered that a participant is pregnant or may have been pregnant at the time of study exposure and through the end of the safety follow-up period the investigator must immediately notify the BMS Medical Monitor/designee of this event and complete and forward a Pregnancy Surveillance Form to the BMS designee within 24 hours of awareness of the event and in accordance with SAE reporting procedures described in Appendix 3.

Follow-up information regarding the course of the pregnancy, including perinatal and neonatal outcome and, where applicable, offspring information, must be reported on the Pregnancy Surveillance Form. Protocol-required procedures for study discontinuation and follow-up must be performed on the participant.

Any pregnancy that occurs in a female partner of a male study participant should be reported to the Sponsor or designee. In order for the Sponsor or designee to collect any pregnancy surveillance information from the female partner, the female partner must sign an ICF for disclosure of this information. Information on this pregnancy will be collected on the Pregnancy Surveillance Form.

9.2.7 Laboratory Test Result Abnormalities

The following laboratory test result abnormalities should be captured on the nonserious AE CRF page or SAE eCRF, as appropriate. Paper forms are only intended as a back-up option when the electronic system is not functioning.

- Any laboratory test result that is clinically significant or meets the definition of an SAE
- Any laboratory test result abnormality that required the participant to have study intervention discontinued or interrupted
- Any laboratory test result abnormality that required the participant to receive specific corrective therapy

It is expected that, wherever possible, the clinical rather than laboratory term would be used by the reporting investigator (eg, anemia vs low hemoglobin value).

9.2.8 Potential Drug Induced Liver Injury (DILI)

All occurrences of potential DILIs, meeting the defined criteria, must be reported as SAEs (see Section 9.2.5 and Appendix 3 for reporting details).

Wherever possible, timely confirmation of initial liver-related laboratory abnormalities should occur prior to the reporting of a potential DILI event. All occurrences of potential DILIs meeting the defined criteria must be reported as SAEs (see Section 9.2 and Appendix 3 for reporting details).

Potential DILI is defined as:

- AT (ALT or AST) elevation > 3 times upper limit of normal (ULN)
 AND
- Total bilirubin > 2 times ULN, without initial findings of cholestasis (elevated serum alkaline phosphatase)

AND

• No other immediately apparent possible causes of AT elevation and hyperbilirubinemia, including, but not limited to, viral hepatitis, pre-existing chronic or acute liver disease, or the administration of other drug(s) known to be hepatotoxic.

9.2.9 Other Safety Considerations

Any significant worsening of conditions noted during interim or final physical examinations, ECG, x-ray filming, or any other potential safety assessment required or not required by the protocol should also be recorded as a nonserious AE or SAE, as appropriate, and reported accordingly.

9.3 Overdose

For this study, any dose of deucravacitinib greater than 2 days' worth of study intervention within a 24-hour time period will be considered an overdose. Overdoses that meet the regulatory definition of SAE will be reported as an SAE (see Appendix 3).

The investigator should do the following in the event of an overdose:

- 1) Contact the Medical Monitor immediately.
- 2) Closely monitor the participant for AEs/SAEs and laboratory abnormalities until deucravacitinib can no longer be detected systemically (at least 3 days).
- 3) Document the quantity of the excess dose as well as the duration of the overdosing in the eCRF.

Decisions regarding dose interruptions or modifications will be made by the investigator in consultation with the Medical Monitor based on the clinical evaluation of the participant.

9.4 Safety

Planned time points for all safety assessments are listed in the Schedule of Activities.

All urgent safety concerns must be discussed with the Sponsor immediately upon occurrence or awareness to determine if the participant should continue or discontinue study intervention.

Safety evaluations that will be performed in addition to AE monitoring are physical examinations, vital signs, ECGs, concomitant medication use, and laboratory tests.

9.4.1 Physical Examinations

A complete physical examination will include general appearance, head, eyes, ears, nose, mouth, throat, neck, extremities, cardiovascular, respiratory, GI/abdomen, lymphatic, musculoskeletal, skin, and psychiatric and neurologic examinations. A targeted physical examination will include any organ system associated with an AE or a laboratory abnormality.

9.4.2 Vital signs

Vital sign assessments include body temperature, respiratory rate, seated blood pressure, and heart rate. Blood pressure and heart rate should be measured after the participant has been resting quietly for at least 5 minutes.

9.4.3 Electrocardiograms

A 12-lead ECG should be performed after the participant has remained supine for at least 5 minutes prior to the ECG; blood samples for laboratory, assessments should be collected after the tracing so that the ECG results remain as accurate as possible. The ECG results will be read by the principal study investigator or a qualified and delegated designee as per local requirements.

9.4.4 Clinical Safety Laboratory Assessments

- Investigators must document their review of each laboratory safety report.
- The assessments to be performed at specified visits are indicated below.

Hematology		
Hemoglobin		
Hematocrit		
White Blood Count, including differential		
Platelet count		
Coagulation Panel ^c		
International Normalized Ratio		
Prothrombin Time		
Partial Thromboplastin Time or Activated Thromboplastin Time		
Chemistry Panel		
Aspartate aminotransferase (AST)	Total Protein	
Alanine aminotransferase (ALT)	Albumin	
Total bilirubin	Sodium	
Direct bilirubin (if total bilirubin > ULN)	Potassium	

Protocol Amendment No.: 02

Date: 29-Aug-2023 55

Alkaline phosphatase	Chloride
Lactate dehydrogenase	Calcium
Creatinine	Phosphorus
Blood Urea Nitrogen (BUN)	Creatine Kinase ^a
Uric acid	Estimated Glomerular Filtration Rate
Glucose (fasting ^b), at specified visits	
Hemoglobin A1c, at specified visits	

IM011134

deucravacitinib

Urinalysis

Protein

Glucose

Blood

Leukocyte Esterase

Specific Gravity

pН

Microscopic examination (reflex if abnormal)

Lipid Panel^b

Cholesterol (total)

High Density Lipoprotein

Low Density Lipoprotein

Triglycerides

Infectious Serology^c

Hepatitis C Antibody confirmed by HCV-RNA testing if required

Hepatitis B Surface Antigen

Hepatitis B Surface Antibody

Hepatitis B Core Antibody

Hepatitis B DNA as required with confirmed HBV infection; see Appendix 9 (Japan only).

Human Immunodeficiency Virus -1 and -2 Antibody

Other Analyses

Pregnancy test (WOCBP only: serum HCG test at Screening, urine HCG test all other visits)

Follicle-stimulating Hormone (to confirm menopausal status)^c

Thyroid-stimulating Hormone c,d

Abbreviations: CK, creatine kinase; DNA, deoxyribonucleic acid; HBV, hepatitis B virus; HCV, hepatitis C virus; RNA, ribonucleic acid; TSH, thyroid-stimulating hormone; ULN, upper limit of normal; WOCBP, women of childbearing potential.

[figure not shown]
Protocol Amendment No.: 02

Date: 29-Aug-2023

^a If $CK > 2.5 \times ULN$, then reflex testing (ie, CK-MB, Troponin I) will be required.

[figure not shown]
b Samples will be collected after the participant has fasted for ≥ 10 hours; fasting not required for samples collected at the Screening visit.

- ^c Performed at Screening.
- $^{
 m d}$ If TSH is above the normal reference range, test free T4; if TSH is below the normal range, test free T4 and T3.

Protocol Amendment No.: 02

Approved v 3.0 930159159 3.0

Protocol Amendment No.: 02 Date: 29-Aug-2023

ate: 29-Aug-2023 59

Approved v 3.0 930159159 3.0

Protocol Amendment No.: 02

[figure not shown]
Date: 29-Aug-2023

61

Protocol Amendment No.: 02

Date: 29-Aug-2023

Clinical Protocol BMS-986165 IM011134 deucrava citinib

Protocol Amendment No.: 02

Approved v 3.0 930159159 3.0

9.9 Other Assessments

It may also be used to support health authority requests for further analysis (refer to

9.10 Health Economics OR Medical Resource Utilization and Health Economics

Health Economics/Medical Resource Utilization and Health Economics parameters will not be evaluated in this study.

10 STATISTICAL CONSIDERATIONS

10.1 Statistical Hypothesis

Let μ_1 and μ_2 be the population means of change from baseline at Week 24 in SALT for 6 mg QD and 6 mg BID dosages of deucravacitinib, respectively, and μ_0 be the population mean of change from baseline at Week 24 in SALT for placebo; the 2 primary hypotheses for this study are:

- 1) $H0_1$: $\mu_1 = \mu_0$ versus $H1_1$: $\mu_1 \neq \mu_0$
- 2) $H0_2$: $\mu_2 = \mu_0$ versus $H1_2$: $\mu_2 \neq \mu_0$

10.2 Sample Size Determination

Approximately 90 participants will be randomized on Day 1 in a 1:1:1 ratio, resulting in 30 participants in each deucravacitinib dose arm (6 mg QD and 6 mg BID) and 30 participants in the placebo arm.

Assuming a 39-point difference in change in SALT score from baseline to Week 24 between both deucravacitinib doses and placebo, and a common standard deviation (SD) of 43 points, the following table presents 2 scenarios on sample size and overall power of the study.

Type I error	Sample Size	Overall Power
0.10	25	93%
0.05	25	88%

Protocol Amendment No.: 02

Date: 29-Aug-2023

Assuming a 15% drop out rate and an overall type I error of 0.10 level:

1) Without multiplicity adjustment for 2 doses to be compared with the placebo, the study overall power with a sample size of 30 in each arm is 93%

2) With Bonferroni adjustment for 2 doses to be compared with the placebo, the study overall power with a sample size of 30 in each arm is 88%

The expected difference (39 points) between deucravacitinib dose and placebo and common SD (43 points) in the change from baseline in the SALT score are based on an average of recently reported data from clinical trials with oral compounds in participants with moderate to severe AA treated with an oral TYK2/JAK1 inhibitor, PF-06700841 (placebo-adjusted mean 49.5 points, 95% confidence interval [CI] [37.1, 61.8]), and with an oral JAK 3 inhibitor, PF-06651600 (placebo-adjusted mean 33.6 points, 95% CI [21.4, 45.7]) compared to placebo.¹⁸

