10.4.2 Primary Efficacy Endpoints

The 2 primary hypotheses, as specified in Section 10.1, will be tested on the overall significance level of 10%. To strongly control the overall type I error at 10% level, the Bonferroni adjustment will be used to adjust multiplicity due to 2 deucravacitinib dose arms to be compared with the placebo arm.

The primary efficacy endpoint (change in SALT score from baseline to Week 24 [Day 169]) will be analyzed on the randomized population using an analysis of covariance (ANCOVA). The ANCOVA model will include treatment arm, the randomization stratification variable of alopecia episode duration (< 4 years and ≥ 4 years), as factors, and baseline SALT score as a covariate.

The primary methodology to impute the missing data will be multiple imputation with the assumption of missing at random.

Additional sensitivity analyses will be further outlined in the SAP.

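### Section 10.2 calls 93% and 88% the overall power, but at 25 per arm they are per-dose power; the 0.10 overall error does not hold for the unadjusted scenario

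*Combined protocol and SAP*

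**What the plan says.** Section 10.1 defines two two-sided comparisons, 6 mg QD and 6 mg BID each against placebo, and introduces them with "the 2 primary hypotheses for this study are".

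Section 10.2 states the effect as "Assuming a 39-point difference in change in SALT score from baseline to Week 24 between both deucravacitinib doses and placebo", with a common SD of 43 points. It then says that "the following table presents 2 scenarios on sample size and overall power of the study". The table has two rows: type I error 0.10, sample size 25, overall power 93%; and type I error 0.05, sample size 25, overall power 88%.

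Below the table, one lead-in governs two list items: "Assuming a 15% drop out rate and an overall type I error of 0.10 level". Item 1 begins "Without multiplicity adjustment for 2 doses to be compared with the placebo, the study overall power" and gives 93% with 30 per arm. Item 2 is the Bonferroni case, where "the study overall power with a sample size of 30 in each arm is 88" percent.

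Section 10.4.2 fixes the planned analysis. The hypotheses "will be tested on the overall significance level of 10" percent, and "To strongly control the overall type I error at 10% level, the Bonferroni adjustment will be used".

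**The concern.** With two primary hypotheses, the power of the study can mean the chance of success on at least one dose or on both. Power for one given dose is a third quantity, normally called per-comparison power. Section 10.2 uses the word overall and does not choose. Because the 39-point effect is assumed for both doses, a joint reading is a natural one. Someone who takes 88% as the chance that both doses succeed, or as the chance that at least one does, would be about 8 points out, in opposite directions.

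The second problem is the shared lead-in. If it applied to item 1, dropping the multiplicity adjustment would gain 5 points of power (93% against 88%) at the same overall error. Two unadjusted tests at 0.10 cannot keep the overall error at 0.10, so the two items are not compared on equal terms.

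**Working it through.** **Inputs, all from Sections 10.1 and 10.2.** Difference 39; SD 43; two-sided tests; 1:1:1 allocation, so both comparisons share the placebo arm; table sample size 25; 30 randomized per arm; 15% dropout.

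**Link between 25 and 30.** 30 × 0.85 = 25.5, and 25 / 0.85 = 29.4, which rounds up to 30. The table's 25 is therefore read as evaluable participants per arm, although it is not labelled so.

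**Step 1: reproduce the printed figures as per-dose power.** For one dose against placebo with n = 25 per arm:

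- Standard error = 43 × √(2/25) = 12.16
- Noncentrality = 39 / 12.16 = 3.207, with df = 2 × 24 = 48
- Two-sided 0.10: critical t = 1.677, power = 93.5%
- Two-sided 0.05: critical t = 2.011, power = 88.1%

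These agree with the printed 93% and 88% to about half a point.

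**Step 2: test the joint definitions at the same n.** Joint power was obtained from 2,000,000 simulated three-arm trials with a shared placebo arm, a 39-point effect in both doses and pairwise t-tests. The last row is a noncentral F calculation.

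| Definition (25 per arm) | 0.10 per test | 0.05 per test |
|---|---|---|
| Printed | 93% | 88% |
| One given dose | 93.5% | 88.1% |
| At least one dose | 98.2% | 95.9% |
| Both doses | 88.8% | 80.4% |
| Global F-test of the three arms | 95.3% | 91.1% |

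Pooling the SD over three arms changes little. At 0.05 it gives 88.5% for one dose, 96.0% for at least one and 81.1% for both.

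**Step 3: look for other settings that give 93/88.** With 30 analysed per arm and no dropout:

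- Both-dose power is 93.9% (0.10) and 88.3% (0.05).
- Per-dose power is 93.2% at 0.05 and 88.4% at 0.025.

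Both pairs come close. Both need 30 evaluable per arm, against the table's 25 and the stated 15% dropout, and the second also needs alphas that are not the table's.

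**Step 4: familywise error under the global null, 25 per arm.**

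- Item 1, each dose at 0.10: 17.5% by simulation. The bivariate normal with correlation 0.5 gives 17.6%. Independent tests would give 1 − 0.90² = 19%, and the Bonferroni bound is 20%.
- Item 2, each dose at 0.05: 9.1%, with a bound of 10%.

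The 0.10 overall level therefore holds for item 2 and fails for item 1.

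**The case against.** The printed numbers are not miscalculated: 93% and 88% are sound as per-dose power. A reader can also see that 0.05 in the table is 0.10 halved for two doses, hence a per-comparison level. Item 1 says openly that it is unadjusted, so the 0.10 in the lead-in might be taken as a nominal starting level, spent whole in item 1 and split in item 2. The list items quote 30 per arm, and at 30 analysed, both-dose power comes close to 93/88. No stated decision rule requires success on both doses, so 80% answers a question the protocol does not ask. Section 10.4.1 leaves technical detail to the SAP, and the text reviewed contains no separate SAP, so a definition there cannot be excluded.

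Much of this stands. It is a labelling fault, the per-dose reading is an inference, and the joint powers are useful only if an overall figure is wanted. Two parts do not stand. The reading at 30 analysed contradicts the section's own 25 and 15% dropout, and a second near-match is itself a reason to define the term. The nominal-level reading conflicts with Section 10.4.2, which uses overall type I error in the familywise sense and brings in Bonferroni to control it. A definition of power in the SAP would not correct the lead-in either.

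**Conclusion.** The point holds and is minor. At the stated sample size and dropout, 93% and 88% are the power of one dose-versus-placebo comparison; neither pair of joint powers, nor the global F-test, reproduces them. If both doses have the 39-point effect, the Bonferroni design has about 88% power per dose, 96% for at least one dose and 80% for both. The claim of a 0.10 overall type I error is wrong for the unadjusted scenario, whose familywise error is about 17.5%; it is right for Bonferroni, at about 9%.

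The power figures assume two-sided pairwise t-tests, 25 evaluable per arm, SD 43 and a shared placebo arm. They do not represent the planned ANCOVA with multiple imputation in all randomized participants. Error control in the planned analysis, the sample size and the choice of test are unaffected.

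**What to change.** Change the wording of Section 10.2 only.

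- **Table.** Rename the columns *two-sided alpha per dose-versus-placebo comparison*, *evaluable participants per arm* and *power per comparison*.
- **Item 2.** For example: *With 30 randomized per arm and 15% dropout (25 evaluable), Bonferroni at two-sided 0.05 per dose keeps the overall type I error at or below 0.10 and gives 88% power per dose.*
- **Item 1.** Take it out from under the 0.10 overall-error statement, or state its familywise error of about 17.5%.
- **Optional, if an overall figure is wanted.** Add that, with a 39-point effect in both doses, power is about 96% for at least one dose and about 80% for both, and give the assumptions (pairwise t-tests, 25 evaluable per arm, SD 43, shared placebo; not the planned ANCOVA with multiple imputation).

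If the sponsor meant another definition of overall power, state it with the sample size used.

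The cost is a few lines of text, with no change to sample size, alpha or the analysis in Section 10.4.2. The one drawback is that the both-dose figure, if added, looks less favourable than 88%.

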10.3 Analysis Sets

For the purposes of analyses, the following populations are defined:

Population	Description
Enrolled	All participants who signed the informed consent.
Randomized	All participants who were in the enrolled population and were randomized using IRT.
Safety	All participants who were in the randomized population and received at least 1 dose of study intervention.

Abbreviations: IRT, Interactive Response Technology.

10.4 Statistical Analysis

10.4.1 General Considerations

All efficacy analyses will be carried out on the randomized population and will be analyzed according to the treatment assigned at randomization.

All safety analyses will be carried out on the safety population and will be analyzed by the actual treatment received.

The statistical analysis plan (SAP) will be developed and finalized before database lock and will describe the selection of participants to be included in the analyses and procedures for accounting for missing, unused, and spurious data. Below is a summary of planned statistical analyses of the primary and secondary endpoints.

Protocol Amendment No.: 02 Date: 29-Aug-2023

The SAP will include a more technical and detailed description of the statistical analyses described in this section. This section is a summary of the planned statistical analyses of the most important endpoints.

A description of the participant population will be included in the clinical study report, including subgroups of age, gender, race, and other study specific populations and demographic characteristics. A description of participant disposition will also be included in the clinical study report.

A database lock will occur once all randomized participants have completed the Week 24 assessments or have discontinued prior to Week 24. Analyses of the collected efficacy and safety results during the 24-week placebo-controlled period will be performed in order to aid in planning for subsequent clinical development. Details of these analyses will be described in the SAP.

10.4.2 Primary Efficacy Endpoints

The 2 primary hypotheses, as specified in Section 10.1, will be tested on the overall significance level of 10%. To strongly control the overall type I error at 10% level, the Bonferroni adjustment will be used to adjust multiplicity due to 2 deucravacitinib dose arms to be compared with the placebo arm.

The primary efficacy endpoint (change in SALT score from baseline to Week 24 [Day 169]) will be analyzed on the randomized population using an analysis of covariance (ANCOVA). The ANCOVA model will include treatment arm, the randomization stratification variable of alopecia episode duration (< 4 years and ≥ 4 years), as factors, and baseline SALT score as a covariate.

The primary methodology to impute the missing data will be multiple imputation with the assumption of missing at random.

Additional sensitivity analyses will be further outlined in the SAP.

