10.4.3 Secondary Efficacy Endpoint(s)

The analyses and summary statistics for all secondary efficacy endpoints, as specified in Table 4-1, will be presented in appropriate tables. The 90% confidence intervals and p values will be provided, as needed, by applying appropriate statistical models to each endpoint that will be specified in detail in the SAP.

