The investigator, Sponsor, or designee should provide the IRB/IEC with reports, updates, and other information (eg, expedited safety reports, amendments, administrative letters) annually, or more frequently, in accordance with regulatory requirements or institution procedures.

Protocol Amendment No.: 02

Approved v 3.0 930159159 3.0

The investigator is responsible for providing oversight of the conduct of the study at the site and adherence to requirements of the following where applicable:

- ICH guidelines,
- United States Code of Federal Regulations, Title 21, Part 50 (21CFR50)
- European Union Directive 2001/20/EC; or
- European Regulation 536/2014 for clinical studies (if applicable),
- European Medical Device Regulation 2017/745 for clinical device research (if applicable),
- the IRB/IEC
- and all other applicable local regulations.

COMPLIANCE WITH THE PROTOCOL AND PROTOCOL REVISIONS

The investigator should not implement any deviation or change to the protocol without prior review and documented approval/favorable opinion of an amendment from the IRB/IEC (and, if applicable, also by the local Health Authority), except where necessary to eliminate an immediate hazard(s) to study participants.

If a deviation or change to a protocol is implemented to eliminate an immediate hazard(s) prior to obtaining relevant approval/favorable opinion(s), the deviation or change will be submitted as soon as possible to:

- IRB/IEC
- Regulatory authority(ies), if applicable by local regulations (per national requirements)

Documentation of approval/favorable opinion signed by the chairperson or designee of the IRB(s)/IEC(s) and, if applicable, also by the local Health Authority, must be sent to Bristol-Myers Squibb (BMS).

If an amendment substantially alters the study design or increases the potential risk to the participant: (1) the ICF must be revised and submitted to the IRB(s)/IEC(s) for review and approval/favorable opinion; (2) the revised form must be used to obtain consent from participants currently enrolled in the study if they are affected by the amendment; and (3) the new form must be used to obtain consent from new participants prior to enrollment.

FINANCIAL DISCLOSURE

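### Plain Bonferroni for the two primary dose comparisons is valid but gives up power: Holm's step-down also controls the error strongly at 10% and raises per-dose power from 88.6% to 92.3% on the plan's inputs

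*Combined protocol and SAP*

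**What the plan says.** Section 10.1 introduces one two-sided hypothesis per dose with the words "the 2 primary hypotheses for this study are". Section 10.4.2 says that they "will be tested on the overall significance level of 10"% and continues: "To strongly control the overall type I error at 10% level, the Bonferroni adjustment will be used to adjust multiplicity". With two comparisons, that means 0.05 for each dose. The protocol text describes no step-down, gatekeeping or alpha-recycling rule.

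Section 10.2 bases the sample size on equal effects: "Assuming a 39-point difference in change in SALT score from baseline to Week 24 between both deucravacitinib doses and placebo", with a common SD of 43, 25 evaluable participants per arm and 15% dropout. It reports 93% power without adjustment. With Bonferroni, "the study overall power with a sample size of 30 in each arm is 88"%. It cites two reference effects, 49.5 and 33.6 points.

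Section 10.4.1 leaves the technical detail to a separate SAP, whose text was not available for this review.

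**The concern.** Bonferroni meets the one criterion that 10.4.2 sets, so this is an efficiency loss and not an error. The loss arises because each dose stays at 0.05 whatever happens to the other. Once one dose has been shown to differ from placebo, only one hypothesis remains, and the full 10% can be spent on it without breaching the overall limit. Holm's procedure does exactly that.

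What is at stake is the second dose. The plan has a primary hypothesis for each dose, Section 3.1 gives choice of dosage as a purpose of the study, and Section 10.4.1 says the Week 24 results will guide later development. Missing an effective second dose is a real cost in a trial of about 90 people. Holm does not change the chance that at least one dose succeeds, and neither rule compares the doses with each other.

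**Working it through.** **Inputs.** Difference 39 points for both doses, SD 43, 25 evaluable per arm, 15% dropout (Section 10.2); overall alpha 0.10 over two tests (Section 10.4.2); two-sided alternatives (Section 10.1).

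**Reproducing the plan's figures.**
- Dropout: 25 / (1 − 0.15) = 29.4, rounded up to 30 per arm.
- Noncentrality: 39 / (43 × √(2/25)) = 39 / 12.16 = 3.21.
- Two-arm t test (48 df): power 88.1% at 0.05 and 93.5% at 0.10.
- Variance pooled over three arms (72 df, closest to the planned ANCOVA): 88.6% and 93.7%.

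The plan's 88% and 93% are therefore power for a single dose, although 10.2 labels them overall power.

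**Does Holm control the error at 10%?**
- Both doses inert: a false rejection needs the smaller p-value to be at or below 0.05, as under Bonferroni. The bound is 0.05 + 0.05 = 0.10.
- One dose inert: it can be rejected only if its own p-value is at or below 0.10, so the bound is 0.10.

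Control is therefore strong, with no assumption about how the two tests are correlated. Every Bonferroni rejection is also a Holm rejection.

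**Power.** Figures come from simulation of 1,000,000 to 2,000,000 three-arm trials per case, with a shared placebo arm, pooled-SD t tests (3n − 3 df) and SD 43 unless stated.

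| Case | Per dose, Bonferroni | Per dose, Holm | Both, Bonferroni | Both, Holm | At least one, either rule |
|---|---|---|---|---|---|
| 39/39 points, n = 25 | 88.6% | 92.3% | 81.1% | 88.6% | 96.0% |
| 39/39 points, n = 30 | 93.5% | 96.0% | 88.8% | 93.8% | 98.2% |
| 33.6/33.6 points, n = 25 | 77.8% | 83.2% | 65.9% | 76.6% | 89.7% |

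That 88.6% appears twice in the first row is coincidence.

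Arithmetic check: with equal effects, per-dose power is the mean of the at-least-one and both-dose figures. First row: (96.0 + 81.1)/2 = 88.6 and (96.0 + 88.6)/2 = 92.3. The per-dose gain is half the both-dose gain: (88.6 − 81.1)/2 = 3.7 or 3.8 points, depending on rounding.

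**Cases where the gain or the price differs (n = 25).**
- ANCOVA with an assumed baseline correlation of 0.5: SD = 43 × √(1 − 0.25) = 37.2. At 39/39 points, per-dose power is 95.5% versus 97.4%, and both-dose power 92.1% versus 95.9%.
- Unequal effects, assuming the two reference values (49.5 and 33.6 points): power for the weaker dose rises from 77.8% to 86.0%.
- One dose at 39 points, the other inert: the effective dose gains only 0.3 points (88.6% to 88.9%). The inert dose is falsely rejected in 5.0% of trials under Bonferroni and 9.1% under Holm. With 49.5 points on the effective dose, the figures are 5.0% and 9.8%.
- Both doses inert: familywise error is about 9% under either rule.

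**Match with confidence intervals.** On the plan's inputs, Holm rejects for both doses where Bonferroni does not in 88.6 − 81.1 = 7.5% of trials. In those trials a 95% interval for the second dose would include zero although Holm rejects.

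**The case against.** The strongest reply is that nothing is broken. Bonferroni delivers the stated control, its 88% power reproduces, and the plan misses no power target. In a preliminary dose-finding trial a sponsor could also reasonably prefer to hold each dose at 5%. Holm adds only second-dose claims judged at 0.10, and it nearly doubles the false-positive rate for an inert dose when the other one works. In that same case the effective dose gains almost nothing. The 3.7-point headline rests on equal effects and ignores covariate adjustment. At an assumed correlation of 0.5 the per-dose gain is 1.9 points. Bonferroni also has simple matching intervals, and the SAP may already refine the rule.

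Much of this stands as qualification. The gain does depend on both doses working, but that is the plan's own assumption, and it is larger for the weaker dose when the effects differ in the way shown above. The higher false-positive rate is real, but it stays within the 10% that the sponsor chose as its limit. The plan states no separate 5% limit per dose as an aim in its own right. The interval mismatch is real and should be declared. The point about the SAP is conditional: as the protocol stands, it names Bonferroni.

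**Conclusion.** The concern holds as a recommended improvement, not as a correction of an error. On the plan's inputs, Holm cuts the chance of missing a given effective dose from 11.4% to 7.7% (100 − 88.6 and 100 − 92.3), about a third, with no added participants and the same 10% strong control. Power for both doses rises by 7.5 points; the chance of at least one success does not change.

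The size rests on 39 points for both doses, SD 43 and 25 evaluable per arm. It ignores covariate adjustment and multiple imputation; the plan's power figures reproduce without either. The gain is smaller if ANCOVA removes much variance and close to nil if one dose is inert. It is larger at the lower reference effect of 33.6 points. The conclusion assumes that the SAP has no step-down rule.

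**What to change.** 1. **Section 10.4.2:** replace the Bonferroni adjustment with the Holm step-down procedure. Test the smaller of the two p-values at 0.05; if it is significant, test the other at 0.10; if it is not, reject neither hypothesis.
2. **Section 10.2:** replace the single 88% with the Holm figures for 25 evaluable per arm: 92% per dose, 89% for both doses and 96% for at least one dose, each labelled as such.
3. **Intervals:** state the confidence level for the primary comparisons. Section 10.4.3 says "The 90% confidence intervals and p values will be provided, as needed", but for secondary endpoints only; 10.4.2 gives no level. Add that an interval may not match the Holm decision for the second dose.
4. **SAP:** carry the same rule, or confirm that a step-down rule is already there.

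The cost is one sentence in 10.4.2 plus the power and interval text. Treatment, visits and sample size do not change. It needs a protocol amendment, since under Appendix 2 the investigator "should not implement any deviation or change to the protocol without prior review and documented approval/favorable opinion of an amendment from the IRB/IEC". It should be in place before the Week 24 database lock, after which designated sponsor staff may see unblinded data. The amendment should state both downsides: the rise from 5% to about 9–10% in false rejection of an inert dose when the other works, and the interval mismatch in about 7.5% of trials on the plan's inputs if 95% intervals are shown.
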